- All subjects will take olaparib by mouth twice daily until disease progression or intolerable side effects
- Subjects will be assessed for safety (continuously) and efficacy (every 6 weeks)
- Subjects will be analyzed in 3 separate comparison groups according to their mutation status
 - Comparison Group 1: Patients with a germline mutation in DNA repair genes
 - Comparison Group 2: Patients with BAP1 somatic mutations
 - Comparison Group 3: Patients with neither germline mutations nor BAP 1 somatic mutations

• Up to 30 evaluable subjects will be enrolled

TABLE OF CONTENTS

| PRÉCIS | |
|----------|---|
| TABLE OF | CONTENTS |
| 1 INT | RODUCTION9 |
| 1.1 S | tudy Objectives |
| 1.1.1 | Primary Objective |
| 1.1.2 | Secondary Objectives |
| 1.2 B | ackground and Rationale9 |
| 1.2.1 | Malignant Mesothelioma |
| 1.2.2 | Preclinical Activity of Olaparib Against Primary Mesothelioma Cell Lines 10 |
| 1.2.3 | Olaparib12 |
| 1.2.4 | Study Rationale |
| 2 ELI | GIBILITY ASSESSMENT AND ENROLLMENT14 |
| 2.1 E | ligibility Criteria |
| 2.1.1 | Inclusion Criteria |
| 2.1.2 | Exclusion Criteria |
| 2.1.3 | Recruitment Strategies |
| 2.2 S | creening Evaluation |
| 2.3 R | egistration Procedures |
| 2.3.1 | Treatment Assignment and Randomization/Stratification Procedures |
| 3 STU | DY IMPLEMENTATION |
| 3.1 S | tudy Design |
| 3.2 D | Prug Administration |
| 3.3 D | Oose Delays/Modifications |
| 3.3.1 | Modifications and Management of Hematologic Toxicities |
| 3.3.2 | Modifications and Management of Non-Hematologic Toxicities |
| 3.4 S | tudy Calendar |
| 3.5 C | riteria for Removal from Protocol Therapy and Off Study Criteria |
| 3.5.1 | Criteria for Removal from Protocol Therapy |
| 3.5.2 | Follow Up |
| 3.5.3 | Off-Study Criteria |
| 3.5.4 | Withdrawal of Informed Consent |

| | 3.5.5 | Off Protocol Therapy and Off-Study Procedure | 29 |
|---|-------|---|----|
| 4 | COl | NCOMITANT MEDICATIONS/MEASURES | 29 |
| | 4.1 S | upportive Care | 29 |
| | 4.2 P | rohibited Medications | 29 |
| | 4.3 P | ermitted with Olaparib Dosing Changes | 30 |
| | 4.3.1 | Strong or Moderate CYP3A inhibitors | 30 |
| | 4.4 P | ermitted with Caution | 30 |
| | 4.4.1 | Strong or Moderate CYP3A inducers | 30 |
| | 4.4.2 | P-gp Inhibitors | 30 |
| | 4.4.3 | Effect of Olaparib on Other Drugs | 30 |
| | 4.5 P | ermitted Medications | 31 |
| | 4.5.1 | Anticoagulant Therapy | 31 |
| | 4.5.2 | Palliative Radiotherapy | 31 |
| 5 | BIO | SPECIMEN COLLECTION | 31 |

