1 INTRODUCTION

1.1 STUDY OBJECTIVES

1.1.1 Primary Objective

- Determine the efficacy with respect to objective response rate of olaparib in patients with malignant mesothelioma based on somatic or germline mutation status of DNA repair genes
- 1.1.2 Secondary Objectives
 - To assess the safety and tolerability of olaparib in patients with mesothelioma
 - To assess progression free survival in patients with mesothelioma treated with olaparib monotherapy
 - To investigate the potential of soluble mesothelin levels and levels of megakaryocyte potentiating factor to predict any therapeutic response

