1.2 BACKGROUND AND RATIONALE

1.2.1 Malignant Mesothelioma

Malignant mesothelioma is an invasive and often fatal neoplasm that arises from mesothelium that lines several organs. Common primary sites of origin of mesothelioma are the pleura (80-90%) and peritoneum (10-15%) and rarely the pericardium and tunica vaginalis.^[1] Among the three

main histologic subtypes of mesothelioma, epithelioid tumors are the most common and have a better prognosis than biphasic and sarcomatoid tumors. Mesothelioma is managed with surgery, usually administered in combination with other modalities of treatment such as chemotherapy or radiation. For patients with unresectable disease, chemotherapy using the regimen of cisplatin plus pemetrexed is the standard of care.^[2] The prognosis of patients with unresectable disease is particularly poor with median survival ranging from 10-13 months.

Up to 20% of mesothelioma cases occur in patients without significant exposure to asbestos. Risk factors in this cohort are not well understood, but include radiation exposure, exposure to non-asbestos mineral fibers such as erionite, simian virus 40, and genetic predisposition.^[1, 3, 4] Recent studies have identified germline mutations in the gene encoding BRCA1 associated protein-1 (*BAP1*) which can predispose to mesothelioma.^[3, 4] In addition to mesothelioma, germline *BAP1* mutations confer increased susceptibility for the development of several other

tumors including uveal melanoma, cutaneous melanoma, renal cell cancers and possibly other cancers.

Using germline DNA from 241 consecutive patients enrolled on a prospective study of natural history of mesothelioma, we have found that a deleterious germline mutation is present in 12% of mesothelioma patients (unpublished data, confidential). In addition to *BAP1*, we found several novel germline variants that have previously not been associated with risk of developing mesothelioma. These include mutations in *CHEK2*, *PALB2*, and *BRCA2*, *MLH1*, *POT1*, *TP53*, *MRE11A*. Figure 1 shows the distribution of germline mutations identified in our cohort.

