1.2.2 Preclinical Activity of Olaparib Against Primary Mesothelioma Cell Lines

Olaparib, a poly(ADP-ribose) polymerase inhibitor (PARPi), targets PARP which is required to repair single strand DNA breaks in homologous recombination (HR) repair pathway. Being a first clinically approved PARPi, it exploits synthetic lethality in patients carrying either *BRCA1* or *BRCA2* germline mutations. BRCA 1 associated protein (BAP1) is a deubiquitinase that functions as a tumor suppressor. In HR DNA repair pathway, BAP1 has been shown to interact with BRCA1.

As evidenced by recent data derived from ovarian and prostate cancer patients, mutations in DNA repair genes can define subgroups of cancer patients with distinct vulnerabilities to DNA damage response inhibitors. Our preliminary results also show that established mesothelioma cell lines as well as primary mesothelioma cell lines established from patients with pleural or peritoneal mesothelioma are sensitive to olaparib.

Figure 2. Expression of *BAP1* in different mesothelioma cell lines. Established breast cancer HCC1937 was used as a control cell line that expresses *BAP1* and has been shown to be resistant to olaparib.

A majority of the mesothelioma cell lines with weak or no BAP1 expression were sensitive to olaparib (Table 1). However, there are exceptions. For example, NCI-Meso19 and NCI-Meso52 which strongly expressed BAP1 were equally sensitive to olaparib while as NCI-Meso44 which had no BAP1 expression was resistant to olaparib. These results suggest that sensitivity of mesothelioma cell lines to olaparib may be dependent on other factors besides BAP1. Since the sensitivity of mesothelioma tumors may not be completely dependent on BAP1 we also plan to enroll patients without BAP1 mutations on the study. However, the mechanisms that lead to decreased BAP1 protein expression are not well-known.

| Cell Line | BAP1 Expression | Olaparib IC ₅₀ (µM) |
|------------------------------|-----------------|-----------------------------------|
| Breast Cancer Cell Line | | |
| HCC1937 | Strong | >50 |
| Established Mesothelioma Cel | l Lines | |
| H2052 | Weak | 30 |
| H2452 | Weak | 40 |
| H28 | No | 18 |
| Patient Derived Mesothelioma | Cell Lines | |
| NCI-Meso16 | No | 23 |
| NCI-Meso17 | Weak | 7 |
| NCI-Meso18 | No | 24 |
| NCI-Meso19 | Strong | 24 |
| NCI-Meso21 | No | 30 |
| NCI-Meso29 | No | 27 |
| NCI-Meso41 | No | 31 |
| NCI-Meso44 | No | >50 |
| NCI-Meso52 | Strong | 5 |

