1.2.4 Study Rationale

Olaparib, a poly(ADP-ribose) polymerase inhibitor, targets PARP which is required to repair single strand DNA breaks in homologous recombination (HR) pathway. Being a first clinically approved PARPi, it exploits synthetic lethality in patients carrying either *BRCA1* or *BRCA2* germline DNA repair mutations. Using germline DNA from 241 consecutive patients enrolled on a prospective study of natural history of mesothelioma, we have found that a deleterious germline

mutation is present in 12% of mesothelioma patients. In addition to *BAP1*, we found several novel germline variants that have previously not been associated with risk of developing mesothelioma. We hypothesize that a subset of mesothelioma patients with germline or somatic alterations in DNA repair genes could benefit from treatment with PARP inhibitors.

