3 STUDY IMPLEMENTATION

3.1 STUDY DESIGN

This is a phase 2, open label, single center study of olaparib in subjects with progressive malignant mesothelioma who have previously been treated. Olaparib will be continued until disease progression or unacceptable toxicity. As indicated in section 10, subjects will be analyzed in 3 separate comparison groups according to their mutation status:

- Comparison Group 1: Patients with a germline mutation in DNA repair genes
- Comparison Group 2: Patients with *BAP1* somatic mutations
- Comparison Group 3: Patients with neither germline DNA repair mutations nor *BAP1* somatic mutations

Germline samples for mutation status analysis will be collected and stored in a CLIA certified laboratory Genetics Branch (CLIA# 21D2125203). Tissue (blocks and slides) and fresh biopsies (if collected) will be stored in the NCI Laboratory of Pathology (CLIA#21D0716664). Genetic analysis will be performed retrospectively using the ClinOmics platform.

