10.2 SAMPLE SIZE DETERMINATION

The primary objective of this pilot study is to obtain preliminary estimates of the overall response rates to olaparib in patients with malignant mesothelioma according to their individual comparison group:

- Comparison Group 1 Patients with a germline mutation in DNA repair genes (estimated at 10-12% of all patients)
- Comparison Group 2 Patients with *BAP1* somatic mutations (estimated at 50-60% of all patients)
- Comparison Group 3 Patients with neither germline DNA repair mutations nor BAP1 somatic mutations (estimated at 30-40% of all patients).

All patients will be enrolled without consideration of their mutation status, and then the results will be retrospectively categorized and evaluated by mutation type. These results will be used to determine if there are any further patients to be enrolled following an amendment taking into consideration the preliminary results obtained.

It would be desirable if overall there was at least approximately a 20% response rate. The study will initially plan to enroll 30 evaluable patients in order to estimate the overall response rate with a maximum two-sided 90% confidence interval width of +/- 16%. If the observed response rate were 15-20%, the confidence interval width overall would be approximately +/-10-15%. Thus, 30 patients are adequate for an overall assessment of response. If during the initial 20 patients evaluated, there are 0-1 responses noted, then no further patients will be enrolled as soon as this can be determined since the upper one-sided 90% confidence interval bound on 1/20 is 18.1%, which is below the approximate response rate of interest. Because accrual is proceeding rapidly on the study and continued enrollment is desirable at this time, up to 25 total patients may be enrolled (5 additional patients) while awaiting the response evaluations among the first 20 patients.

It is expected that 30 evaluable patients can be enrolled in approximately 12-18 months. As patient non-compliance with study drug dosing will prevent them from being evaluable, the accrual ceiling must be adjusted accordingly. Estimating an average of 3 cycles of study therapy and a non-compliance rate of 10% per cycle the accrual ceiling will be set at 40 patients.

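### Do the comparison groups need redefining because the objective covers any somatic DNA-repair mutation and Groups 1 and 2 can overlap?

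*Combined protocol and SAP*

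**What the plan says.** The primary objective (section 1.1.1) is response to olaparib "based on somatic or germline mutation status of DNA repair genes". The rationale (section 1.2.4) supposes that "a subset of mesothelioma patients with germline or somatic alterations in DNA repair genes could benefit from treatment with PARP inhibitors".

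Section 3.1 says that "subjects will be analyzed in 3 separate comparison groups according to their mutation status". Sections 10.1 and 10.2 give the groups and their expected shares:

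- Group 1: a germline mutation in a DNA-repair gene, 10-12%.
- Group 2: a somatic BAP1 mutation, 50-60%.
- Group 3: "Comparison Group 3 Patients with neither germline DNA repair mutations nor BAP1 somatic mutations (estimated at 30-40% of all patients".

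The précis words the last group slightly differently: "Comparison Group 3: Patients with neither germline mutations nor BAP 1 somatic mutations".

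The response rates overall and in the three groups are the primary endpoints (section 10.1.1). Each group rate is reported with a 95% confidence interval, and the results inform whether more patients are added by amendment (section 10.4.2). Section 3.1 states that "Genetic analysis will be performed retrospectively using the ClinOmics platform". Sections 10.4.7 and 10.4.9 plan no subgroup or exploratory analyses.

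**The concern.** Two things look wrong.

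First, the objective and the hypothesis speak of somatic alterations in DNA-repair genes generally, but BAP1 is the only somatic criterion in the groups. A patient whose sole alteration is a somatic mutation in another repair gene falls into Group 3, the group meant to have no relevant alteration, and no planned analysis separates such patients. Section 1.2.2 itself allows that "sensitivity of mesothelioma tumors may not be completely dependent on BAP1 we also plan to enroll patients without BAP1 mutations".

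Second, the groups are called separate, yet a germline carrier with a somatic BAP1 mutation meets the definitions of both Group 1 and Group 2. No order is given, and no closed gene list defines Group 1, although section 5.3 describes the germline test as whole exome.

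The group rates are primary endpoints in an open-label trial with investigator-assessed response, and the genetics are read retrospectively. An unstated placement rule could therefore be settled once responses are known. With so few germline carriers expected, one placement could move the Group 1 rate a long way.

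**Working it through.** **1. Reproduce the plan's shares.** Inputs from section 10.2: Group 1 is 10-12%, Group 2 is 50-60%, Group 3 is 30-40%, and N = 30. If Groups 1 and 2 do not overlap, Group 3 is the remainder:

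- Lowest: 100 − 12 − 60 = 28%.
- Highest: 100 − 10 − 50 = 40%.

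This agrees with the stated 30-40% to within 2 points, so the plan treats the groups as a partition. The stated ranges sum to 90% at the low ends (10 + 50 + 30) and 112% at the high ends (12 + 60 + 40). They are too loose to yield an overlap figure.

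Expected numbers: Group 1 is 30 × 0.10 = 3.0 to 30 × 0.12 = 3.6. Group 2 is 30 × 0.50 = 15 to 30 × 0.60 = 18.

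**2. Size of the overlap.** The documents give none. At the extremes it runs from 0 to all of Group 1, that is 0 to 3.6 of 30. If germline and somatic BAP1 status are assumed independent:

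- Overlap: 30 × 0.10 × 0.50 = 1.5 to 30 × 0.12 × 0.60 = 2.16 patients.
- Group 3: (1 − 0.12) × (1 − 0.60) = 35.2% to (1 − 0.10) × (1 − 0.50) = 45%.

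**3. What each placement does, under independence.**

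| Placement of patients meeting both | Group 1 | Group 2 |
|---|---|---|
| Germline first | 3.0 to 3.6 | 30 × 0.50 × 0.88 = 13.2 to 30 × 0.60 × 0.90 = 16.2 |
| Counted in both | 3.0 to 3.6 | 15 to 18 |
| BAP1 first | 30 × 0.10 × 0.40 = 1.2 to 30 × 0.12 × 0.50 = 1.8 | 15 to 18 |

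**4. Which placement fits the plan.** Section 1.2.1 reports, from 241 consecutive patients, that "we have found that a deleterious germline mutation is present in 12% of mesothelioma patients". That is a count of carriers whatever their somatic status. Group 1's 10-12% matches it. BAP1 first would make Group 1 only 1.2/30 = 4% to 1.8/30 = 6%. So the stated share points to keeping every germline carrier in Group 1. What then remains open is whether 1.5 to 2.2 patients also stay in Group 2, which is 10-12% of that group.

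**5. Effect on the Group 1 estimate.** Take the unfavourable case: 3 germline carriers, one responder, and that responder also has a somatic BAP1 mutation. Exact 95% intervals:

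- Kept in Group 1: 1/3 = 33.3% (0.8 to 90.6%).
- Moved to Group 2: 0/2 = 0% (0 to 84.2%).

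The point estimate moves, but the intervals overlap almost entirely. The contrast also needs the BAP1-first order, which step 4 finds a poor fit.

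**6. The somatic criterion.** BAP1 is the only somatic marker in all four definitions (précis, 3.1, 10.1, 10.2). Section 1.2.2 builds its laboratory case on BAP1 expression. The other genes named in section 1.2.1 (CHEK2, PALB2, BRCA2, MLH1, POT1, TP53, MRE11A) are germline findings, and carriers of repair-gene mutations among them belong to Group 1. No frequency is given for somatic mutations in other repair genes, so the number of such patients in Group 3 cannot be calculated and may be zero. Section 5.3 states exome breadth for the blood sample only, so it is not known whether the tumour assay would find them.

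**7. What does not depend on placement.** The overall response rate, the precision statement for 30 patients and the rule for 0-1 responses in the first 20 use all evaluable patients. No between-group test is planned, and no threshold is set on any group rate.

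**The case for a change.** The strongest case for a change is that a primary endpoint should have a defined denominator before the data are seen, and that a small sample is no excuse for leaving one open. The overlap is also unlikely to be empty: under independence, the chance that at least one of 3 or 4 germline carriers also has a somatic BAP1 mutation is 1 − 0.5³ = 87.5% to 1 − 0.4⁴ = 97.4%. Listing the groups as 1, 2 and 3 is not an assignment rule. The share argument is an inference too, since by the same logic 50-60% could describe all patients with somatic BAP1 mutations. The pathogenicity terms in section 5.3.1 govern return of results, not grouping.

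Most of this stands as a description of the text: the plan contains no explicit order and no closed gene list. It does not show harm. Keeping germline carriers in Group 1, with or without counting them again in Group 2, gives the same Group 1 denominator. Only the order that fits the stated share poorly changes it. The group rates are called preliminary estimates, and further enrolment needs an amendment, at which point individual cases would be open to inspection.

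On the somatic side, a separate row within Group 3 would add a subgroup of unknown size that depends on an unspecified assay. It would not improve the planned estimates.

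**Conclusion.** No change follows. The missing placement order and gene list are gaps that analysts would fill sensibly: germline carriers to Group 1, the remaining patients with somatic BAP1 mutations to Group 2, all others to Group 3. This reading rests on matching the 10-12% share to the 12% carrier rate, which is an inference and not a written rule. The overlap of 1.5 to 2.2 of 30 rests on assumed independence; without that assumption it lies anywhere from 0 to 3.6.

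The broader wording of section 1.1.1 is loose drafting. Sections 10.1 and 10.2 restate the primary objective by comparison group, and the BAP1-only criterion is applied consistently. The précis's omission of DNA repair in Group 3 is a clerical slip, since sections 3.1, 10.1 and 10.2 all include it.

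The consequence is confined to descriptive group rates. For Group 1, at 3 to 4 patients, the interval is too wide under any placement to support a conclusion.

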3.2 DRUG ADMINISTRATION

Olaparib at the dose of 300 mg will be given orally continuously twice daily, with doses taken at the same times each day approximately 12 hours apart. The correct number of 100mg or 150mg tablets comprising the appropriate dose should be taken at the same times each day with approximately 240 mL of water. Doses may be taken with a light meal/snack. The olaparib tablets should be swallowed whole and not chewed, crushed, dissolved, or divided.

Olaparib will be dispensed at the start of each 21-day cycle. Per the CCR policy for selfadministered oral investigational agents (PM-8) which will be followed in this protocol, patients will be provided with a pill diary (Appendix C), instructed in its use, and asked to bring it with them to each appointment.

Patients should be given clear instructions on how and when to take their study treatment. Patients will self-administer olaparib. Study site staff will make tablet counts at regular intervals during treatment. Compliance will be assessed by the tablet count and the information will be recorded in the appropriate section of the eCRF. All patients must return their bottle(s) of olaparib at the appropriate scheduled visit, when a new bottle will be dispensed. Patients will be instructed to notify study site personnel of missed doses. Dates of missed or held doses will be recorded by the patient on their patient diary and by the site staff on the eCRF.

If a patient misses more than 50% of the doses in any given cycle, the patient will be considered inevaluable for response per sections 10.3.2 and 10.3.3 and will be removed from the study.

Patients must return all containers and any remaining tablets at the end of the study.

If vomiting occurs shortly after the olaparib tablets are swallowed, the dose should only be replaced if all of the intact tablets can be seen and counted. Should any patient enrolled on the study miss a scheduled dose, the patient will be allowed to take the scheduled dose up to a maximum of 2 hours after that scheduled dose time. If greater than 2 hours after the scheduled dose time, the missed dose should not be taken, and the patient should take their allotted dose at the next scheduled time. Subjects should avoid grapefruit juice while on study, due to P450 interactions.

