6.3.2 Genomic Data Sharing Plan

Unlinked genomic data will be deposited in public genomic databases such as dbGaP in compliance with the NIH Genomic Data Sharing Policy.

6.4 **Response Criteria**

For the purposes of this study, patients should be re-evaluated for response every 6 weeks (2 cycles). In addition to a baseline scan, confirmatory scans should also be obtained no less than 4 weeks following initial documentation of objective response.

Response and progression will be assessed by the investigator on the basis of physical examinations, computed tomography (CT) or Magnetic Resonance (MR) scans, and potentially other modalities according to standard of care.

For peritoneal mesothelioma, the international criteria proposed by the revised Response Evaluation Criteria in Solid Tumors (RECIST) guideline (version 1.1)^[17] will be used. Changes in

the largest diameter (unidimensional measurement) of the tumor lesions and the shortest diameter in the case of malignant lymph nodes are used in the RECIST criteria.

For pleural mesothelioma, modified RECIST for MPM (malignant pleural mesothelioma)^[18] should be used as described in section 6.4.2.

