10.3 POPULATIONS FOR ANALYSES

10.3.1 Evaluable for Toxicity

All patients will be evaluable for toxicity from the time of their first treatment with olaparib.

10.3.2 Evaluable for Objective Response, Progression Free Survival and Soluble Mesothelin Levels and PFS

Only those patients who have measurable disease present at baseline, have received at least one cycle of therapy, have taken at least 50% of the doses per given cycle, and have had their disease re-evaluated will be considered evaluable for response. These patients will have their response classified according to the definitions stated below. (Note: Patients who exhibit objective disease progression prior to the end of cycle 1 will also be considered evaluable.)

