10.4 STATISTICAL ANALYSES

10.4.1 General Approach

Response rates will be determined in all patients and in the three comparison groups, based on all evaluable patients, and reported along with appropriate confidence intervals.

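### Is the interim enrolment limit of 25 too small to deliver the 20 evaluable patients that the futility rule needs?

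*Combined protocol and SAP*

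**What the plan says.** Section 10.2 sets the interim rule: "If during the initial 20 patients evaluated, there are 0-1 responses noted, then no further patients will be enrolled". The reason given is that the one-sided 90% upper bound on 1/20 is 18.1%, below the rate of interest of roughly 20%. Because accrual is fast, "up to 25 total patients may be enrolled (5 additional patients) while awaiting the response evaluations among the first 20 patients". Section 10.4.6 repeats both statements.

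The next paragraph of 10.2 deals with losses: "As patient non-compliance with study drug dosing will prevent them from being evaluable, the accrual ceiling must be adjusted accordingly". It assumes an average of 3 cycles of therapy and "a non-compliance rate of 10% per cycle the accrual ceiling will be set at 40 patients", for a target of 30 evaluable.

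Three other places bear on who counts:

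- Section 3.2: if more than half the doses of any cycle are missed, "the patient will be considered inevaluable for response per sections 10.3.2 and 10.3.3 and will be removed from the study".
- Section 10.3.2: patients with measurable disease who have received at least one cycle, "have taken at least 50% of the doses per given cycle, and have had their disease re-evaluated will be considered evaluable for response". Objective progression before the end of cycle 1 also makes a patient evaluable.
- Section 10.4.1: response rates are "based on all evaluable patients, and reported along with appropriate confidence intervals".

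Under section 6.4, response is reassessed every 6 weeks, which is 2 cycles. A response is confirmed by a scan at least 4 weeks after it is first seen.

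**The concern.** The figure of 25 is 20 + 5, with no attrition term, although the paragraph that follows adjusts the overall target for exactly that attrition. If the 20 are evaluable patients, as 10.3.2, 10.4.1 and the denominator of the 18.1% bound suggest, and the 25 are enrolled patients, then 25 may not yield 20. Accrual would then be held while the team waited for evaluations that the enrolled patients could not supply. Otherwise the team would have to choose, with responses already known, between enrolling past 25 and applying the rule to a smaller set.

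This is the trial's only planned interim look, so an improvised decision at that point would be unwelcome. A smaller set also weakens the rule's stated justification, because the upper bound rises as the denominator falls.

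**Working it through.** **Inputs.** From 10.2: target 30 evaluable, ceiling 40, 10% loss per cycle, 3 cycles, rule on 20, limit of 25, rate of interest about 20%. From 6.4: first scheduled scan after 2 cycles. Assumption added here: losses and responses are independent, between patients and of each other.

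**The plan's own figures.** Retention over 3 cycles is 0.9³ = 0.729, and 30/0.729 = 41.2, close to the stated 40. The ceiling itself implies 30/40 = 0.75. The exact (Clopper-Pearson) one-sided 90% upper bound on 1/20 is 18.1%, as stated.

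**Enrolled against evaluable.** For retention p, the enrolment needed on average for 20 evaluable is 20/p, the expected number evaluable among 25 is 25p, and the chance of falling short is P(Bin(25, p) ≤ 19).

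| Retention p | Basis | 20/p | 25p | Chance of fewer than 20 |
|---|---|---|---|---|
| 0.729 | 3 cycles | 27.4 | 18.2 | 71% |
| 0.75 | 30 of 40 | 26.7 | 18.8 | 62% |
| 0.81 | 2 cycles, to first scan | 24.7 | 20.3 | 33% |
| 0.90 | 1 cycle | 22.2 | 22.5 | 3% |

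The shortfall therefore depends on counting all 3 cycles. Even then it is about 2 patients on average (27.4 − 25 = 2.4; 26.7 − 25 = 1.7). Since 25 − 20 = 5, up to 5 of the 25 (20%) can be lost with 20 still evaluable.

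**When the shortfall matters.** Accrual stops only on 0 or 1 responses. Once two evaluable patients have responded, the rule cannot trigger, and the remaining evaluations are not needed to settle it. The rule stays open only if fewer than 20 of the 25 are evaluable and at most 1 has responded. For a true response rate r, that chance is the sum over e = 0 to 19 of P(Bin(25, p) = e) × P(Bin(e, r) ≤ 1):

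| Retention p | r = 20% | r = 10% | r = 5% |
|---|---|---|---|
| 0.729 | 8.5% | 34% | 56% |
| 0.75 | 7.1% | 29% | 49% |
| 0.81 | 3.4% | 15% | 26% |

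For comparison, with 20 evaluable patients the rule stops accrual with probability P(Bin(20, r) ≤ 1) = 7% at r = 20%, 39% at 10% and 74% at 5%. An unresolved rule is thus likely mainly at low response rates, where stopping is the intended outcome.

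**If the rule were applied to a short set.** The same bound on 1 response is 19.0% for 1/19, 19.9% for 1/18 and 21.0% for 1/17. The stated rationale holds down to 18 evaluable and fails at 17. The chance that 25 enrolled give 17 or fewer is P(Bin(25, p) ≤ 17) = 36% at 0.729, 27% at 0.75 and 9% at 0.81.

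**The other reading of 25.** The précis and 10.2 both attach the verb enrol to evaluable patients when giving the target of 30, and 10.2 then shortens this to 30 patients. Read the same way, 20 and 25 are both evaluable counts. The matching accrual is 25/0.75 = 33.3 or 25/0.729 = 34.3, below the ceiling of 40, and nothing conflicts.

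**The case for a change.** The best argument for a change is that 3 cycles is the plan's own figure. Section 3.2 makes a patient inevaluable for missing doses in any cycle, so losses can continue after the first scan. A response first seen at week 6 cannot be confirmed before week 6 + 4 = 10, after 3 cycles (9 weeks) have ended. On that basis 25 enrolled would more likely than not (62% to 71%) give fewer than 20 evaluable. Nothing in the plan says whether inevaluable patients among the first 20 are replaced, and a sentence or two would settle it.

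The arithmetic stands, and so does the silence on replacement. Three things limit its force:

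- The later timing concerns patients awaiting confirmation of a response. Those who progress early count as evaluable under 10.3.2, which moves retention towards the higher values.
- The conflict requires 20 to be evaluable and 25 to be enrolled within one sentence, although the plan elsewhere uses enrol for evaluable counts.
- The 62% to 71% is the chance of a short set, not of an undecided rule.

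At response rates of 5% to 10% the undecided case is not rare. What remains then is to evaluate a few replacement patients, for whom the ceiling of 40 leaves room.

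**Conclusion.** No change to the plan follows. Sections 10.2 and 10.4.6 leave two details unstated: whether 20 and 25 count enrolled or evaluable patients, and whether inevaluable patients are replaced. The sensible working is available from the plan itself: apply the rule to the first 20 patients evaluable under 10.3.2, let the additional patients stand in for any who drop out of that set, and stay within the ceiling of 40.

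On the least favourable reading the gap is about 2 patients. The chance that it leaves the rule undecided at the 20% rate of interest is about 3% to 9%, for retention between 0.81 and 0.729. It rises to 15% to 34% at a 10% response rate and 26% to 56% at 5%. All these figures assume independent losses and responses. The 0-1 boundary, the 18.1% bound, the target of 30 and the ceiling of 40 are unaffected, and the trial is a pilot aimed at estimation. An explicit sentence would be tidier, but its absence does not undermine the interim rule.
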